1.0 OBJECTIVES

1.1 *Primary Objective:*

“To evaluate the feasibility and outcomes of a research pre-, peri-, and post-transplant optimization program (R-POP) to improve multiple domains of health including physical function, cognitive function, mental health, and diet and nutrition for patients planning to undergo or undergoing hematopoietic stem cell transplantation (HCT)”

1.2 *Secondary Objectives:*

1.2.1 Gather information on how the following parameters affect hematopoietic stem cell transplant patients’ outcomes and wellness/quality of life:

- physical function and activity,
- cognitive function,
- mental health,
- diet and nutrition,
- social support,
- caregiver support,
- microbiota diversity, and
- biomarkers of inflammation and frailty.

1.2.2 Compare additional clinical endpoints to include:

- overall survival,
- disease-free survival,
- rates of bacterial, fungal, and viral infections as well as overall infections,
- rates of hospital and intensive care unit admission/re-admission and length of stay,
- graft-versus-host disease
- transplant length of stay,
- return to work,
- falls,
- delirium,
- quality of life

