1.2.3 Compare caregiver quality of life

2.0 BACKGROUND, RATIONALE

Hematopoietic stem cell transplantation (HCT) is a complex medical treatment that causes significant symptom burden for patients and their caregivers. Patients receive chemotherapy and/or radiation therapy prior to transplant to eradicate the underlying disease and provide immunosuppression. While the myelosuppressive or myeloablative conditioning regimens used prior to transplant provide medical support to treat underlying disease and provide immunosuppression, they can cause the development of physical,¹ psychological,² and nutritional challenges³⁻⁵ that can impact a patient’s short- and long-term wellness. Allogeneic HCT is associated with treatment related mortality (TRM) ranging from 20-30%.⁶ TRM is particularly high in patients with advanced age, decreased functional status, and/or comorbid conditions such as depression or organ dysfunction. While evaluation of organ dysfunction is required part of pre-transplant workup (echocardiogram, pulmonary function testing, etc.), decreased physical function, cognitive deficits, depression, poor nutrition, and lack of

A Research Program Targeting Pre-, Peri-, and Post-transplant Optimization Program (R-POP)

Version 1.18: October 25, 2022

social support are less often evaluated. This investigation will assess these five domains and implement interventions to improve them.

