4.7.2 Hematopoietic Cell Transplantation-Comorbidity Index (HCT-CI)

From the HCT-CI website, <http://www.hctci.org/>:

“The HCT-CI was initially designed using clinical data from 1055 consecutive patients treated with allogeneic HCT from 1997 to 2004 at the Seattle Cancer Care Alliance (SCCA)/Fred Hutchinson Cancer Research Center (FHCRC).¹¹⁹ The index was validated among patients transplanted at the SCCA/FHCRC,¹²⁰ as well as other transplant institutions world-wide.¹²¹ {Barba, 2010 #1383,122} Multi-institutional validation of the predictive power of the HCT-CI is ongoing. The HCT-CI was shown to be an important decision-making instrument for choosing appropriate conditioning regimens for patients with acute myeloid leukemia or myelodysplastic syndromes¹²³ and those with lymphoma or chronic

A Research Program Targeting Pre-, Peri-, and Post-transplant Optimization Program (R-POP)

Version 1.18: October 25, 2022

lymphocytic leukemia.¹²⁴ The HCT-CI together with the degree of severity of blood cancer could be used to stratify outcomes of patients 60 years or older who were treated with a minimally-toxic nonmyeloablative conditioning regimen and allogeneic HCT.¹²⁵ Recently, a combined HCT-CI/age index was designed and validated that takes into account the burden of comorbidities as well as increasing age in risk-assessment.¹²⁶

HCT-CI is evaluated on all allogeneic transplant patient candidates as part of our clinical standard of care. HCT-CI will be reviewed as part of this study.

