6.0 STATISTICAL CONSIDERATIONS

General Considerations: All analyses will be summarized using appropriate effect estimates, confidence intervals, and p-values. All secondary and additional analyses will be evaluated at the standard 0.05 significance level. Descriptive statistics, including graphical displays, will be used to summarize all study variables. For continuous variables, means, standard deviations, percentiles, ranges, box plots and histograms will be generated. For categorical variables, frequencies and proportions will be generated. For time to event variables, event rates and survival curves will be generated. Statistical analyses will be performed using SAS for Windows (Version 9.3 or above: SAS Institute, Cary, NC) and the R statistical computing platform (R Core Team 2013; <http://www.R-project.org/>).

Categorical outcomes will be analyzed using chi-square techniques and logistic regression modeling. Length of stay outcomes will be analyzed using generalized linear models with appropriate link functions. Continuous, longitudinal outcomes such as the FACT-BMT and EQ-5D-5L will be analyzed using linear mixed regression modeling. Other continuous results (such as PG-SGA and numbers of days exercised and amount of exercise per day) will be analyzed using standard t-test approaches and correlated with outcomes. We will analyze TRM and CTCAE using Kaplan-Meier methods, log-rank tests, and Cox proportional hazard regression modeling.

6.1 Analysis of the Microbiota:

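### PG-SGA and amount of exercise are to be correlated with outcomes with no covariate named, so baseline illness may appear as a benefit of exercise or nutrition

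*Combined protocol and SAP*

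**What the plan says.** Section 6.0 of the combined protocol and SAP takes three measures together, "Other continuous results (such as PG-SGA and numbers of days exercised and amount of exercise per day", and states that they "will be analyzed using standard t-test approaches and correlated with outcomes". It does not say which outcomes, which time point, which coefficient or which groups the t-test compares. No adjustment is mentioned.

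Regression is named for other outcome types in the same section: "Categorical outcomes will be analyzed using chi-square techniques and logistic regression modeling", generalized linear models for length of stay, linear mixed models for FACT-BMT and EQ-5D-5L, and for TRM and adverse events "Kaplan-Meier methods, log-rank tests, and Cox proportional hazard regression modeling". None of these lists a covariate. On testing, "All secondary and additional analyses will be evaluated at the standard 0.05 significance level".

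The purpose is set out in objective 1.2.1: "Gather information on how the following parameters affect hematopoietic stem cell transplant" patients' outcomes, with physical activity and nutrition among the parameters. Section 2.0 says that "TRM is particularly high in patients with advanced age, decreased functional status, and/or comorbid conditions such as depression or organ dysfunction".

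The baseline risk measures are collected. HCT-CI is in the Section 4.0 assessment table at new patient evaluation (NPE), age is recorded (Section 7.0), and cardiopulmonary exercise testing precedes training (Section 4.1.1). The only stated use of the comorbidity index, in Section 4.7.2, is that "HCT-CI will be reviewed as part of this study".

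**The concern.** A t-test and a simple correlation cannot separate the exposure from the patient's condition at entry. The protocol's own account gives reason to expect the two to be mixed.

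- **Risk and outcome.** Section 2.0 links age, function and comorbidity to TRM. Section 7.0 repeats the link for poor function and frailty.
- **Risk and PG-SGA.** Section 4.4.1 shows that the total score includes sections on disease and on metabolic demand. Illness is therefore part of the exposure measure itself.
- **Risk and exercise.** Section 4.1.1 scales intensity to each patient's fitness, but three sessions a week is a maximum and most sessions are done independently. Volume can therefore follow what a patient is able to do. This link is reasoned; the documents do not quantify it.

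The study has one arm, and Section 2.9 asks whether better health before transplant leads to better outcomes after it. A crude correlation between exercise and outcome, tested at 0.05, could be read as an answer to that question when it partly reflects who was well enough to exercise.

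**Working it through.** The plan gives no effect size, power or correlation for these analyses, so there is no figure to reproduce. The check asks how often a crude correlation would be significant if exposure and outcome shared only baseline illness.

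**Inputs**
- n = 30. Sections 3.5 and 6.2 expect 35 consented and 30 in the intervention. Patients not cleared leave the study (Section 3.2), so 30 is used for PG-SGA as well.
- Significance level 0.05 (Section 6.0). Two-sided is assumed, because the sidedness of these tests is not stated.
- a = size of the correlation between baseline illness and exposure; b = size of the correlation between baseline illness and outcome. Both are assumptions, shown as a range.
- TRM of 10–30% (Section 7.0; Section 2.0 gives 20–30%).

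**Crude correlation.** With no true effect, the expected size is r = a × b. At n = 30 (28 degrees of freedom, t = 2.048), significance needs |r| of at least 2.048 / √(28 + 2.048²) = 0.361. A simulation with 40,000 replicates per row gave:

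| a = b | a × b | Mean crude r | Share with p<0.05 |
|---|---|---|---|
| 0.2 | 0.04 | 0.04 | 5.4% |
| 0.3 | 0.09 | 0.09 | 7.6% |
| 0.4 | 0.16 | 0.16 | 13.7% |
| 0.5 | 0.25 | 0.25 | 27.2% |
| 0.6 | 0.36 | 0.36 | 51.2% |
| 0.7 | 0.49 | 0.48 | 81.0% |

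The Fisher z approximation agrees: 13%, 26% and 50% at 0.4, 0.5 and 0.6.

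**After adjustment, confounder measured without error.** The partial correlation is (r_xy − r_xc·r_yc) / √[(1 − r_xc²)(1 − r_yc²)]. In the same simulation its mean was about 0.00 and its false-positive rate 4.9–5.1% in every row.

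**After adjustment, confounder measured imperfectly.** Suppose the risk index correlates 0.6 with true baseline risk (an assumption) and a = b = 0.5. The index then correlates 0.6 × 0.5 = 0.30 with exposure and with outcome. The partial correlation is (0.25 − 0.09) / (1 − 0.09) = 0.18. By Fisher z at n = 30 with one covariate, about 15% reach p<0.05. That is better than about 27%, but not 5%.

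**Events for TRM.** 0.10 × 30 = 3 and 0.30 × 30 = 9, so about 3–9 deaths. That is too few to fit the exposure with HCT-CI, age and VO2peak together.

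**The case against.** The strongest reply is that the plan never calls these analyses unadjusted. Section 6.0 names several regression models that could carry exercise or PG-SGA as predictors along with covariates. This stands in part: what the text supports is that no adjustment set is named, and that the two methods assigned to these measures have no place for one.

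A reader might infer that baseline illness will show up as a treatment effect. The documents do not support that certainty. They give neither correlation, and at 0.2 or 0.3 the excess of false positives is slight. Several features could weaken the link with exercise: the cardiac exclusions and the exclusion of patients unable to exercise, physician clearance after exercise testing (Section 3.2), and intensity set relative to fitness.

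A reader might also infer that these correlations are the only evidence on exercise and outcome, or that they will drive the next trial. Neither is established. Exercise and physical-function testing is repeated within patients. Section 7.0 says that success of this feasibility study would inform a randomized phase 2 trial, and no decision rule is tied to a correlation.

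Finally, adjustment is only a partial remedy. The combined HCT-CI/age index appears only in quoted background text in Section 4.7.2, without scoring. Nor does a baseline covariate correct for patients who fall ill later and then exercise less. Both points stand, and they shape the fix.

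**Conclusion.** The point holds in a limited form. For PG-SGA, days exercised and amount of exercise, Section 6.0 names methods that cannot account for baseline risk, although the objective is worded in terms of effect and suitable baseline measures are already collected. Confounding may produce apparent benefit.

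With 30 patients and no true effect, the share of significant crude correlations runs from about 5% to about 81% across assumed links of 0.2 to 0.7. Which part of that range applies cannot be told from the documents. The calculation assumes one baseline factor, equal links to exposure and outcome, linear relations and two-sided tests.

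Only secondary, exploratory analyses are affected. The primary hypothesis in Section 6.2, on the share of patients completing more than half of their sessions, does not depend on them.

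**What to change.** In Section 6.0:

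1. Name the outcomes and time points to be related to PG-SGA and to exercise.
2. For continuous outcomes, replace the simple correlation with a regression on the exposure, adjusted for one baseline risk term: HCT-CI, or HCT-CI combined with age, with the scoring stated. Add VO2peak at NPE for the exercise analyses.
3. Measure the exposure in a window that ends before the outcome period, for example NPE to sign-off, because baseline adjustment does not remove illness that develops later.
4. Report crude and adjusted estimates side by side with confidence intervals, and call both associations.
5. For TRM, use at most the single risk term and present the result as descriptive.

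The change is to analysis wording; the variables are already collected. It costs one or two degrees of freedom. Residual confounding remains if the index measures risk imperfectly, and the report should say so.

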4.8 Safety endpoints

Treatment-related mortality (TRM) and grade 3-4 adverse events as defined by the National Cancer Institute Common Terminology Criteria for Adverse Events (NCI-CTCAE) ¹³⁵ will be monitored that are related to study interventions (e.g. exercising).

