7.0 DATA SAFETY MONITORING PLAN

Throughout the study, we will collect data on treatment-related mortality (TRM) and grade 1-4 adverse events as defined by the National Cancer Institute Common Terminology Criteria for Adverse Events (NCI-CTCAE)¹³⁵ will be monitored during weekly or monthly assessments, that are related to study interventions (e.g. Exercising).

For all the above assessments and interventions, data will be obtained using electronic surveys through RedCap or in person assessments (e.g. CPET testing) and entered into RedCap. While the medical record number will be kept by study staff to enable access to the medical record for event monitoring and data abstraction, data will be entered and stored using a coded study number; likewise biospecimens will be stored under this coded study number as opposed to the patient medical record number. Other identifiable information include treatment dates (e.g. date of new patient evaluation, date of study evaluations, transplant date, etc.).

Use of previously collected biospecimens, data, or records

As part of this study, we will obtain data from the patient's medical record (see above section). Study staff will abstract this information using the patient's medical record number and enter the data into RedCap as above.

Potential risks to subjects with study interventions, procedures, or interactions

This is a low risk intervention study that does not involve the use of a study drug or investigational device. We do not anticipate any major toxicities occurring with participation in our investigation. The study interventions are evidenced-based and aimed at improving any health concerns the participants may have. As with all studies, there is a potential risk of loss of privacy and confidentiality associated with all study procedures. These are addressed in the below section on protection against risks.

Additional risks with patient assessments and interventions:

Short physical performance battery – abstracted from records, no additional risk

6 minute walk – abstracted from records, no additional risk

30 second sit/stand – abstracted from records, no additional risk

Grip strength – abstracted from records, no additional risk

Fried - abstracted from records, no additional risk

PROMIS Physical Function – questionnaire/survey, minimal risk

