Incidental findings related to cardiopulmonary concerns (e.g. CPET testing or interval training) would lead to notification of the primary provider and referral to cardiology or other appropriate services.

Incidental findings related to nutritional status are part of the goal of this study and, the primary provider will be notified.

Incidental findings related to psychological distress, depression, lack of social support, etc. (e.g. raised by questionnaires/surveys) would lead to notification of the primary provider and referral to psychology, psychiatry, social work, or other appropriate services.

Incidental findings related to cognitive function (e.g. raised by questionnaires/surveys) would lead to notification of the primary provider and referral to neuropsychology, occupational therapy, or other appropriate services.

c. Vulnerable Subjects

As this study is built around the Duke Adult Bone Marrow Transplant Program, which only treats patients age 18 and older, fetuses, neonates, and children will be excluded. While subjects may be as old as 80 years, adults with cognitive impairment and unable to consent to participation will not be enrolled. Pregnant women are excluded from transplant and will therefore be excluded from this study. Prisoners and institutionalized individuals are also excluded from this study.

Potential Benefits of the Proposed Research to Research Participants and Others

Potential benefits to research participants

A Research Program Targeting Pre-, Peri-, and Post-transplant Optimization Program (R-POP)

Version 1.18: October 25, 2022

Studies have shown that patients with poor function (e.g. depression, physical frailty) prior to transplant have worse outcomes after transplant (e.g. increased treatment-related mortality). By addressing these functional domains during the pre-transplant period (median 101 days), we have the opportunity to both improve function as well as patient outcomes.

In addition, this study may identify issues pertaining to caregiver distress, leading to the development of further studies targeted at caregivers.

Why the risks to subjects are reasonable in relation to the anticipated benefits

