Risks to subjects are reasonable in that risks are low (e.g. related to exercise or psychological distress associated with questionnaire) and the goal of this study is to address these and other risks that may be raised. In fact, it is potentially beneficial to identify and address these risks prior to transplant than during the stress of transplant when they may emerge.

Importance of the Knowledge to be Gained

Importance of the knowledge to be gained

The success of this feasibility study would inform the development of a randomized phase 2 trial of pre-transplant interventions to improve transplant outcomes. This could establish a new standard of care for the treatment of transplant patients.

Why the risks to subjects are reasonable in relation to the importance of the knowledge that reasonably may be expected to result

Treatment-related mortality with allogeneic transplant ranges from 10-30%, with more frail individuals (i.e. functional impairment) at higher risk of adverse events. This study is low risk and has the potential to lead to new interventions to reduce treatment related mortality, which would have a significant impact on health.

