7.1 Adverse Events Reporting

While this is a low risk exercise intervention study that does not involve the use of a drug or medical device, the PI will be responsible for the identification and documentation of adverse events and serious adverse events, as defined below. At each study visit or assessment, the PI or designee must assess, through non-suggestive inquiries of the subject or evaluation of study assessments, whether an Adverse Event or Severe Adverse Event has occurred.

An adverse event (AE) is any untoward medical occurrence in a subject receiving study intervention and which does not necessarily have a causal relationship with this treatment. For this protocol, the definition of AE also includes worsening of any pre-existing medical condition. An AE can therefore be any unfavorable and unintended or worsening sign (including an abnormal laboratory finding), symptom, or disease temporally associated with the use of study intervention, whether or not related to use of the study intervention. Abnormal laboratory findings without clinical significance (based on the PI's judgment) should not be recorded as AEs. But laboratory value changes that require therapy or adjustment in prior therapy are considered adverse events.

Serious adverse events (SAEs) are adverse events that result in any of the following outcomes: death, life-threatening adverse event in the view of the investigator its occurrence places the patient at immediate risk of death, inpatient hospitalization or prolongation of existing hospitalization, a persistent or significant incapacity

or substantial disruption of the ability to conduct normal life functions, or a congenital anomaly/birth defect. All SAEs will be reported to the DUHS IRB within 24 hours for life-threatening events and within 5 business days for non-life-threatening events

From the time the subject signs the informed consent form through the End of Study visit, all AEs/SAEs must be recorded in the subject adverse events case report form. AEs will be assessed according to the CTCAE version 4.0. If CTCAE grading does not exist for an AE, the severity of the AE will be graded as mild (1), moderate (2), severe (3), life-threatening (4), or fatal (5).

In addition to severity, all AEs will be graded as:

- Definite: The AE is clearly related to the study intervention
- Probably: The AE is likely related to the study intervention
- Possible: The AE may be related to the study intervention

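### Section 6.0 names Kaplan-Meier for TRM, a cause-specific endpoint, with no competing-risk method; if 1-KM is read as the probability of TRM it is too high in expectation, and the sense of TRM needs stating once (minor)

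*Combined protocol and SAP*

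**What the plan says.** Section 6.0 gives the only analysis rule for TRM and adverse events: "We will analyze TRM and CTCAE using Kaplan-Meier methods, log-rank tests, and Cox proportional hazard regression modeling". Its general paragraph adds: "For time to event variables, event rates and survival curves will be generated". Nowhere does the document mention competing risks or cumulative incidence, or say how deaths that are not TRM are handled.

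TRM has no formal definition. Section 4.8 lists TRM and grade 3-4 adverse events as safety endpoints that "will be monitored that are related to study interventions (e.g. exercising"). Section 7.0 repeats this for TRM and grade 1-4 events, to be monitored "during weekly or monthly assessments, that are related to study interventions (e.g. Exercising"). The background (2.0) and the risk justification in 7.0 use the same term for mortality of allogeneic transplant, at 20-30% and 10-30% respectively.

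Section 7.1 sets the recording window: "From the time the subject signs the informed consent form through the End of Study visit, all AEs/SAEs must be recorded". It also gives a five-level scale of relatedness to the study intervention. Section 3.5 describes a single-arm study, and 6.2 plans 35 consented patients with 30 taking part in the intervention.

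**The concern.** Kaplan-Meier estimates a probability correctly when patients censored at a given time have the same later risk as those still followed. A patient who has died of something else has no later risk of TRM. Censoring that death treats the patient as still able to have the event, so 1-KM answers a hypothetical question: how much TRM there would be if nobody could die otherwise. Relapse raises the same problem if the adopted definition excludes deaths after relapse.

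The second difficulty is that section 6.0 cannot be carried out without choosing what TRM means. Transplant-related and intervention-related death differ in starting point, denominator, competing events and expected number of events.

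What is at stake is modest: the reported size of a named safety endpoint in a study that 6.2 describes as one of safety and feasibility, and whose results are meant to inform a randomized phase 2 trial.

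**Working it through.** **Plan's own figure.** The document states no estimate, event count, time horizon or power for TRM, so there is nothing to reproduce.

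**Inputs.** TRM of 10-30% (7.0) and 20-30% (2.0); 30 patients in the intervention (6.2). The competing incidence is not in the documents; 5-30% over the same period is an assumption, as are constant hazards.

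**Direction on the same data.** With d TRM deaths among Y at risk at each event time:
- cumulative incidence = sum of S(t-) × d/Y, where S is survival free of any event;
- 1-KM = sum of S1(t-) × d/Y, where S1 counts TRM only and censors other events.

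S(t-) never exceeds S1(t-), so 1-KM is never below the cumulative incidence estimate. The two are equal if no competing event precedes a TRM death.

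**Large-sample size.** With true TRM F1 and competing incidence F2, 1-KM = 1 - (1 - F1 - F2)^(F1/(F1+F2)). For F1 = 0.20 and F2 = 0.30 this is 1 - 0.5^0.4 = 0.242.

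| True TRM | F2 = 5% | 10% | 20% | 30% |
|---|---|---|---|---|
| 10% | 10.3% | 10.6% | 11.2% | 12.0% |
| 20% | 20.6% | 21.2% | 22.5% | 24.2% |
| 30% | 30.9% | 31.8% | 34.0% | 36.8% |

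**A concrete case.** Take 30 patients, fully followed, with 6 TRM deaths and 9 competing events. If all TRM deaths come first, 1-KM = 6/30 = 20.0%. If all competing events come first, it is 6/21 = 28.6%. Over random orders it averages 24.2%. Cumulative incidence is 20.0% in every order.

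**Against sampling error.** The standard error of a proportion at n = 30 is √(0.1×0.9/30) = 5.5 points at 10%, √(0.2×0.8/30) = 7.3 at 20% and √(0.3×0.7/30) = 8.4 at 30%. The largest excesses in the table are 2.0, 4.2 and 6.8 points. The exact 95% CI for 6/30 is 7.7-38.6%.

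**Against the true probability.** Trials of 30 or 35 patients were simulated with constant hazards, TRM of 10-30% and competing incidence of 10-40%, 2,000 per setting. 1-KM was never below the cumulative incidence estimate, but it fell below the true probability in 15-49% of trials. With TRM set at 1%, as an assumption for intervention-related death, 1-KM exceeded the cumulative incidence estimate in only 18-28% of trials; in most of the rest there was no TRM event and both were zero.

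**Events under each sense.** Transplant-related: 30 × 0.10 to 30 × 0.30 = 3 to 9, if all 30 are transplanted. Intervention-related: few or none, since section 5.0 anticipates no major toxicity. For 0/30 the exact upper 95% limit is 1 - 0.025^(1/30) = 11.6%.

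**The case against.** The strongest reply is that the fault is conditional and small. The plan does not say that 1-KM will be reported. Its promise of event rates could be met by a simple proportion, which with complete follow-up equals the cumulative incidence. Cox regression with other deaths censored is a valid analysis of the cause-specific hazard. Safety oversight does not rest on the curve: adverse events are recorded from consent, monitored continuously by the principal investigator and reviewed annually by the oversight committee. All of this stands, and it limits the point to how a Kaplan-Meier curve for TRM would be read. It does not remove it, because Kaplan-Meier is the only estimator named for this endpoint.

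The reply also bears on the definition. Sections 2.0 and 7.0 quote transplant mortality as background and rationale, and those ranges feed no calculation. In 4.8 and 7.0 the phrase on relatedness may govern TRM and the adverse events together, or the adverse events alone. A reader might infer that the plan fixes two contradictory definitions; the text supports only an ambiguity.

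A reader might also infer that the plan leaves out deaths during pre-transplant training, which falls in what 7.0 calls "during the pre-transplant period (median 101 days"). No section starts the TRM clock at transplant, so this is a caution for whoever sets the clock, not an error in the plan.

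**Conclusion.** The point holds as a minor one. Section 6.0 pairs a cause-specific endpoint with Kaplan-Meier and names no competing-risk method. If competing events are censored and 1-KM is read as a probability, it overestimates TRM in expectation: by 0.3 to 6.8 points for TRM of 10-30%, under constant hazards and an assumed 5-30% competing incidence. With no competing events the excess is zero.

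Two stronger readings are tempting and should be resisted. One is that 1-KM can never be below the true probability of TRM. The inequality is exact only against the cumulative incidence estimate from the same data; a single small sample often falls below the truth. The other is that the reported TRM will be too high whichever sense applies. If TRM is intervention-related, the two estimates will usually coincide, and the useful result is the count with its exact limit.

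No decision rule uses TRM, the excess is within sampling error at 30 patients, and the primary adherence analysis is unaffected. The reason to act is that this error has a known direction and costs almost nothing to remove.

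**What to change.** - **4.8 and 7.0:** state once which sense of TRM applies, with its time origin and denominator. If the clock starts at transplant, report any pre-transplant death separately. Reconcile the grade 3-4 and grade 1-4 wording for adverse events.
- **6.0, transplant-related TRM:** replace Kaplan-Meier with the cumulative incidence function and 95% CI. Deaths that do not meet the TRM definition compete. Relapse or progression competes only if the adopted definition excludes deaths after relapse and the disease can relapse; section 3.1 admits non-cancer illness.
- **6.0, intervention-related TRM:** report the count with an exact CI among patients who start the intervention. Patients not cleared after exercise testing leave the study (3.2), so the 35 consented would not all be followed.
- **6.0, adverse events:** estimate time to first event of the reconciled grades by cumulative incidence, with death competing.
- **6.0, tests and models:** drop the log-rank test for TRM or name the subgroups it compares, since the study is single arm. Treat any Cox result as an exploratory cause-specific hazard, given about 3-9 events at most.
- Keep Kaplan-Meier for overall and disease-free survival.

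The cost is wording in three sections and a little analysis time. Deaths are already recorded as serious adverse events, relapse is already needed for disease-free survival (1.2.2), and the SAS and R named in 6.0 can fit cumulative incidence.
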